### **Overall Design**

This is a Phase 4, single-arm, open-label study to evaluate the efficacy and safety of ravulizumab in adult participants with PNH who switch from eculizumab 1200 mg every 2 weeks (q2w; ie, above the recommended dose) to ravulizumab (at the recommended dose).

The study will consist of a Screening Period of approximately 3 months and a Treatment Period of 351 days. All participants must provide informed consent prior to any procedures at the first Screening visit. All participants must have been prescribed and are receiving a stable dose of eculizumab 1200 mg q2w for at least 3 months prior to screening. During Screening, eculizumab may be administered at the participant's home at the discretion of the Investigator. During screening, participants will continue to receive eculizumab 1200 mg q2w, and blood samples will be collected for PD parameters and lactate dehydrogenase (LDH) levels.

Eligible participants will receive a loading dose of ravulizumab on Day 1, followed by maintenance doses on Day 15 and every 8 weeks (q8w), administered by intravenous (IV) infusion. Ravulizumab loading and maintenance doses will be based on participants' body weight per approved dose regimen. Ravulizumab dosing will be administered in the clinic by a trained member of the site study team; patients may have the option to receive study drug remotely at a medical facility that is located near the patient's home or at the patient's home by a qualified healthcare personnel.

The schedule of study visits and assessments is shown in Section 1.3.

An interim analysis will be performed on Day 183.

**Disclosure Statement:** This is a single-arm, open-label study.

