#### **Data Monitoring Committee: No**

#### 1.2. Schema

- a. Ravulizumab loading dose is 2400 mg for patients weighing ≥ 40 to < 60 kg, 2700 mg for patients weighing ≥ 60 to < 100 kg, or 3000 for participants weighing ≥ 100 kg.
- b. Ravulizumab maintenance dose is 3000 mg for patients weighing ≥ 40 to < 60 kg, 3300 mg for patients weighing ≥ 60 to < 100 kg, or 3600 mg for participants weighing ≥ 100 kg.

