# 4. STUDY DESIGN

### 4.1. **Overall Design**

This is a Phase 4, multicenter, single-arm, open-label study to evaluate safety and efficacy of ravulizumab in adult participants with PNH who switch from eculizumab 1200 mg q2w to ravulizumab.

The study will consist of a Screening Period of approximately 3 months and a Treatment Period of 351 days.

Approximately 20 participants will be enrolled. Eligible participants will be administered eculizumab 1200 mg q2w optionally at home at the discretion of the Investigator, and preference of the patient (see Section 8) during the Screening Period followed by a loading dose of ravulizumab on Day 1, and maintenance treatment with ravulizumab on Day 15 and q8w thereafter until Day 351. Ravulizumab loading and maintenance doses will be based on the participant's body weight measured at the prior visit, per approved dosing regimen. Ravulizumab dosing will be administered in the clinic by a trained member of the site study team; patients may have the option to receive study drug remotely at a medical facility that is located near the patient's home or at the patient's home through a qualified healthcare personnel (see Section 8.11). The schedule of study visits and assessments is shown in Section 1.3.

An interim analysis will be performed on Day 183.

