9.3.1. PK Parameters Summarization

C_{max} and C_{trough} will be summarized descriptively using n, arithmetic mean, SD, CV%, minimum, median, maximum, geometric mean, and geometric CV%.

Accumulation ratio will be calculated for both C_{max} and C_{trough} following the first and last maintenance dose of ravulizumab.

This document is confidential

SAP Version: 2.0 09-Feb-2023

Controlled Document ID: 3903A.02, Effective Date 31-Aug-2020

Attainment of steady state will be calculated using the slope, corresponding 95% CI, and P-value of Ctrough values at Days 15, 71, 127, 183, 239, 295, and 351.

The model will be used to assess whether steady state was achieved for ravulizumab where sufficient data are available. Aggregate assessment of trough concentrations by repeated measures ANOVA will be used to evaluate attainment of steady state. The approach is based on the comparison of log-transformed trough concentration values to the mean of the results for all the succeeding doses up to Day 351.

Repeated measures analysis will be carried out on log-transformed trough levels (predose concentrations) for Days 15, 71, 127, 183, 239, 295, and 351.

The example SAS code will be:

PROC MIXED DATA=xx;

CLASS dose time patient id;

MODEL log(PK parameter) = treatment treatment*time / DDFM=KR;

REPEATED / TYPE=UN SUBJECT=patient_id(dose);

LSMEANS dose*time;

RUN;

The DDFM = KR (KenwardRoger) option performs the degrees-of-freedom calculations detailed by Kenward and Roger (1997). As recommended the denominator degrees of freedom for the fixed effects will be estimated as the most appropriate method in the mixed-model analysis.

Contrasts will be tested between a particular time point and the pooled mean over all remaining time points:

Day 15 / the average pre-dose Day 71 through Day 351

Day 71 / the average pre-dose Day 127 through Day 351

Day 127 / the average pre-dose Day 183 through Day 351

Day 183 / the average pre-dose Day 239 through Day 351

Day 239 / the average pre-dose Day 295 through Day 351

Day 239 / the average pre-dose Day 351

The first non-significant comparison will be concluded to be the day number (Day x) at which steady state concentrations are attained. The p-value for difference of Least Square Means (LSM), LSM Ratio, and the 95% confidence interval for the contrasts will be provided.

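### SAP 9.3.1 fits one trough slope through the Day 15 post-loading level and the 8-week maintenance troughs, so Day 15 dominates the slope; the example code also needs repair

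*SAP*

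**What the plan says.** Protocol 4.1 sets out a "loading dose of ravulizumab on Day 1, and maintenance treatment with ravulizumab on Day 15 and q8w thereafter until Day 351". Protocol 1.2 gives loading doses of 2400, 2700 or 3000 mg and maintenance doses of 3000, 3300 or 3600 mg by weight band.

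SAP 9.3 limits the PK parameter outputs to four, one of which is attainment of steady state. SAP 9.3.1 assesses it in two ways:

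- From the "slope, corresponding 95% CI, and P-value of Ctrough values at Days 15, 71, 127, 183, 239, 295, and 351".
- From a repeated-measures model on log predose levels for the same seven days, with contrasts of each day against the mean of the later days. The sequence begins with "Day 15 / the average pre-dose Day 71 through Day 351", and the first non-significant contrast names the steady-state day.

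No term, exclusion or note sets Day 15 apart. The same section calculates the accumulation ratio after the first and last maintenance doses.

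The example code contains "MODEL log(PK parameter) = treatment treatment*time / DDFM=KR" and "REPEATED / TYPE=UN SUBJECT=patient_id(dose"), lists dose, time and patient identifier in `CLASS`, and requests least-squares means for `dose*time`.

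**The concern.** A slope through troughs is a useful check on steady state when the troughs come from one regimen. Here the first of the seven values follows a different dose by a quarter of the interval (14 days against 56). It also sits at one end of the time axis, where a point has high leverage on a fitted line. A significant slope may therefore reflect only the step from the loading phase to the first maintenance trough, while the maintenance troughs themselves are flat.

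The SAP reports the slope with its interval and p-value beside the contrasts and does not say which prevails if they disagree. A significant slope would naturally be read as steady state not attained. The example code matters because it is the only explicit statement of the model's terms and covariance structure.

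**Working it through.** **1. The SAP's list of days.** Day 1 + 14 = 15. Adding 56 repeatedly gives 71, 127, 183, 239, 295 and 351, which reproduces the list. Time since the previous dose is 14 days at Day 15 and 56 days at each later trough on the 8-weekly schedule. The preceding dose is 600 mg lower at Day 15 in every weight band (3000 − 2400, 3300 − 2700, 3600 − 3000).

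**2. Size of the mismatch.** Assumptions: one compartment, the 60 to <100 kg band (L = 2700 mg, M = 3300 mg), and half-life as shown, since the documents give no figure. With k = ln 2 / half-life, and amounts in mg so that volume cancels in ratios:

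- Day 15: C15 = L·exp(−14k)
- Each later trough: C(next) = (C + M)·exp(−56k)
- Steady-state trough: Css = M·exp(−56k) / [1 − exp(−56k)]

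At 30 days, exp(−14k) = 0.7236 and exp(−56k) = 0.2742. So C15 = 1954, Css = 3300 × 0.2742 / 0.7258 = 1247, and C15/Css = 1.57. Next, C71 = (1954 + 3300) × 0.2742 = 1441, which is 1.16 times Css.

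| Half-life (days) | Day 15 / Css | Day 71 / Css | Day 127 / Css | First trough within 5% of Css |
|---|---|---|---|---|
| 30 | 1.57 | 1.16 | 1.04 | Day 127 |
| 35 | 1.26 | 1.09 | 1.03 | Day 127 |
| 40 | 1.05 | 1.02 | 1.01 | Day 71 |
| 45 | 0.90 | 0.96 | 0.98 | Day 71 |
| 50 | 0.79 | 0.90 | 0.96 | Day 127 |
| 60 | 0.63 | 0.81 | 0.90 | Day 239 |

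**3. How much of the slope is Day 15.** The seven days have mean 183 and deviations −168, −112, −56, 0, 56, 112 and 168, with sum of squares 87,808. In a least-squares log slope per 56 days, Day 15 has weight −168 × 56 / 87,808 = −0.107. Its contribution is that weight times ln(C15/Css):

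- 30 days: −0.107 × ln 1.57 = −0.048 of a total of −0.060, about 80%.
- 35 days: −0.107 × ln 1.26 = −0.025 of −0.031, about 80%.
- 50 days: −0.107 × ln 0.79 = +0.025 of +0.033, about 76%.

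Without Day 15 these slopes fall from −6.0% to −2.4%, from −3.1% to −1.4%, and from +3.3% to +1.8%.

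**4. Chance of a significant slope.** Simulation: 20 participants, independent log residuals with assumed SD 0.25, a least-squares slope per participant, and a two-sided 5% t-test on the 20 slopes. The PK/PD row of Protocol 1.3 Table 2 marks no sample on Days 239 and 295, so the scheduled series is Days 15, 71, 127, 183 and 351. Both series are shown.

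| Half-life (days) | SAP's seven days | Same without Day 15 | Five scheduled days | Same without Day 15 |
|---|---|---|---|---|
| 20 | 1.00 | 0.81 | 1.00 | 0.70 |
| 30 | 1.00 | 0.41 | 1.00 | 0.33 |
| 35 | 0.80 | 0.16 | 0.69 | 0.13 |
| 40 | 0.10 | 0.05 | 0.08 | 0.05 |
| 45 | 0.25 | 0.08 | 0.19 | 0.08 |
| 50 | 0.85 | 0.24 | 0.75 | 0.19 |
| 60 | 1.00 | 0.77 | 1.00 | 0.64 |

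**5. The code, line by line.**

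- The least-squares means are requested for `dose*time`, but `MODEL` holds only treatment and treatment-by-time.
- `treatment` is absent from `CLASS` and has one level in a single-arm study.
- `REPEATED` names no time effect. With an unstructured covariance, rows are placed by order, so a missed trough with no data row moves later ones into the wrong position.
- The subject is the patient nested in `dose`. If `dose` varies within a participant, that person is split into independent subjects.

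**The case against.** The strongest reply is that Day 15 belongs to the process being studied. In the recursion above, C(n) − Css = (C15 − Css)·exp(−56kn), so the Day 15 level is the starting value of the maintenance sequence. Each deviation from steady state is a fixed fraction of the one before: 0.274 at 30 days, 0.379 at 40 and 0.524 at 60. If Day 15 equals the steady-state trough, so does every later trough. This stands. A reader might infer that Day 15 carries no information about steady state, or that naming Day 15 as the steady-state day must be wrong because no maintenance dose has yet been given. The documents do not support either inference: bringing levels there early is something a loading dose can do. At 40 to 45 days Day 15 is 1.05 to 0.90 times steady state, and a null first contrast is roughly the right answer. A significant first contrast only moves the sequence to Day 71, and no later contrast uses Day 15.

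The reply does not rescue the slope. A line across all the days turns one early departure into an apparent trend over the year.

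It is also fair that the code is labelled as an example, with placeholders, and that programming would expose some of its faults. A reader might infer from the nested subject that the first contrast's standard error is badly inflated. That would require `dose` to mean the dose behind each trough, which the SAP never says. If it is a label constant within participant, nothing is split at Day 15.

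**Conclusion.** The point holds for the slope and for the code. The mismatch of dose and interval at Day 15 is fact and needs no model. Its effect rests on the assumed half-life, one-compartment kinetics, a common half-life for all participants and a log-SD of 0.25. At 30, 35 and 50 days, maintenance troughs are within 5% of steady state by Day 127, yet the slope is significant in 69% to 100% of simulated trials on the five scheduled days, against 13% to 33% without Day 15.

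The effect is not uniform. Near 40 days it almost vanishes. At 60 days a significant slope is correct, since troughs do not come within 5% until Day 239. At 20 days Day 71 alone still makes the slope significant in most trials. Starting at Day 71 therefore reduces the problem without removing it. Some of the fall in significance is also lost precision, although the slope estimate itself drops to between 40% and 55% of its value (2.4/6.0 and 1.8/3.3).

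This is a supportive PK output in an estimation study and does not touch the primary endpoint. Correction is worthwhile because it is cheap.

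**What to change.** In SAP 9.3.1:

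- Start the slope and the maintenance steady-state contrasts at Day 71. This is the first maintenance trough, and the one the accumulation ratio already implies.
- Report Day 15 descriptively as the post-loading trough. Its contrast with later days may be kept if labelled as a check of loading-dose adequacy.
- Show the results with and without troughs from participants switched to 6-weekly dosing. Simply deleting those troughs would remove data selectively from participants who had free C5-related breakthrough hemolysis.
- Replace the code with `CLASS patient_id time; MODEL log_conc = time / DDFM=KR; REPEATED time / SUBJECT=patient_id TYPE=UN;` and `ESTIMATE` statements for the listed contrasts.

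The cost is a few lines of SAP text and code, with no new data and no change to treatment. The downside is one fewer time point in the slope, and so less power to detect a real drift: at a 60-day half-life, 0.64 instead of 1.00 on the scheduled days.

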6.1. General Methods

All data collected will be presented using summary tables, figures, and data listings. All data, as well as any outcomes derived from the data, will be presented in detailed data listings. Graphical displays may also be provided, when appropriate. All analyses will be performed using SAS® release, version 9.4 or higher (SAS Institute Inc., Cary, NC, USA) or other validated statistical software. Continuous variables will be summarized using descriptive statistics, including the number of observations, and mean, standard deviation (SD), median, minimum, and maximum values. Categorical variables will be summarized by frequency counts and the percentage of participants. All statistical tests performed will be based on a 2-sided 5% level of significance unless otherwise specified. All participants entered into the database will be included in participant data listings. All relevant participant data will be included in listings.

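### SAP 9.3.1 takes the first non-significant trough contrast as the day steady state is reached, so less precise data tend to give an earlier day while troughs are still changing

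*SAP*

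**What the plan says.** SAP 9.3.1 fits a repeated-measures model to log trough concentrations: "Repeated measures analysis will be carried out on log-transformed trough levels (predose concentrations) for Days 15, 71, 127, 183, 239, 295, and 351". Each log trough is contrasted with the average of all later troughs, the last being Day 351. The decision rule is: "The first non-significant comparison will be concluded to be the day number (Day x) at which steady state concentrations are attained". SAP 6.1 sets the level: "All statistical tests performed will be based on a 2-sided 5% level of significance unless otherwise specified".

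Estimates accompany the test: "The p-value for difference of Least Square Means (LSM), LSM Ratio, and the 95% confidence interval for the contrasts will be provided". The section also plans a slope of trough values with a 95% CI and p-value. Neither the ratio, its CI nor the slope has a stated role in naming Day x. The model is confined to situations with sufficient data, but sufficiency is not defined.

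The list of contrasts ends with "Day 239 / the average pre-dose Day 351", directly after another contrast that also starts from Day 239. The example code requests "LSMEANS dose*time", while its MODEL line contains only `treatment` and `treatment*time`.

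SAP 3.3 plans about 20 participants. SAP 13 plans an interim analysis of the first 10 through Day 183, for publication, with all tables, figures and listings included. The steady-state output is not excepted.

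**The concern.** A non-significant result can mean that a trough is close to the later ones, or that the data are too imprecise to show that it is not. The rule gives both the same conclusion. With ordinary sampling error, reducing the sample or increasing the noise raises the chance that an early contrast fails to reach significance, and hence the chance of an early Day x.

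SAP 9.3 reports only four PK results: Ctrough, Cmax, accumulation ratio and attainment of steady state. A definite Day x could be published from 10 participants at the interim and then move later at the final analysis merely because the sample is larger. The problems with the contrast days and the code mean that part of the planned sequence also cannot be run as written.

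**Working it through.** **The plan's own figures.** No sample size, power, trough SD or margin is given for the steady-state rule. The only precision figures in the SAP are the exact 95% CIs in section 3.3. These reproduce in all seven rows (for example 0/20 gives 0-16.8%, 5/20 gives 8.7-49.1%), but they concern the breakthrough-hemolysis proportion and say nothing about troughs.

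**Inputs from the documents.** Two-sided 5% test (SAP 6.1); n about 20 (SAP 3.3); n = 10 with data through Day 183 (SAP 13); each log trough against the mean of later ones (SAP 9.3.1).

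**Assumed, not in the documents.** Within-participant log SD s = 0.2 to 0.3; independent within-participant errors; no missing samples; true shortfall of 10% or 15% relative to the mean of the m later troughs.

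**One contrast.** SE = s × √((1 + 1/m)/n); effect = −ln(1 − shortfall), which is 0.105 for 10% and 0.163 for 15%; noncentral t with n − 1 df. The probability of non-significance is the probability that |t| stays below the critical value.

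*Final analysis, n = 20, m = 4* (for example Day 15 against Days 71, 127, 183 and 351). SE = 0.2 × √(1.25/20) = 0.050, or 0.075 at s = 0.3. Critical t = 2.093.

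| Shortfall | Noncentrality (s = 0.2; 0.3) | P(non-significant) |
|---|---|---|
| 10% | 2.11; 1.40 | 48%; 73% |
| 15% | 3.25; 2.17 | 13%; 46% |

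*Interim, Day 71, n = 10, m = 2* (Days 127 and 183). SE = 0.2 × √(1.5/10) = 0.077, or 0.116. Critical t = 2.262.

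| Shortfall | Noncentrality (s = 0.2; 0.3) | P(non-significant) |
|---|---|---|
| 10% | 1.36; 0.91 | 77%; 87% |
| 15% | 2.10; 1.40 | 53%; 76% |

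To isolate sample size, keep m = 4 and set n = 10: 73-86% for a 10% shortfall and 46-72% for 15%. This case is hypothetical, since the interim has at most three later troughs (Day 15 against Days 71, 127 and 183).

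**Whole sequence.** A simulation (10,000 runs per setting; paired t-tests standing in for the mixed model) used only the q8w PK days in Protocol Table 2: 15, 71, 127, 183 and 351. Assumed true troughs were 70% of plateau on Day 15 and 80% on Day 71, with the remaining gap halving every 56 days. Runs with no declaration were counted as Day 351.

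| n (log SD 0.25) | Declared at Day 15 or 71 | Mean declared day |
|---|---|---|
| 40 | 5% | 149 |
| 20 | 31% | 118 |
| 10 | 72% | 75 |
| 6 | 90% | 47 |

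At n = 20 the mean declared day is 161, 118, 82 and 51 for log SD 0.15, 0.25, 0.35 and 0.50. The true curve is the same throughout. If troughs are flat from Day 15, the rule names Day 15 in about 95% of runs at n = 20, 10 or 6.

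**Contrast days against the schedule.** The PK/PD row of Protocol Table 2 is marked on Days 1, 15, 71, 127, 183 and 351 and at unscheduled visits. It is blank on Days 239 and 295. A participant on q8w dosing therefore has no scheduled trough for either contrast that starts from Day 239. The Day 183 contrast has one scheduled later trough (Day 351), not three. Values on the two unscheduled days could come only from participants on q6w dosing or from unscheduled visits.

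**Code.** `dose*time` is not in the MODEL statement, and MODEL uses `treatment` where CLASS lists `dose`. The listed contrasts cannot come from this code as written.

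**The case against.** The strongest reply is that this is one descriptive PK output in an estimation study. No dosing, efficacy or safety decision in the documents uses Day x. Every ratio is reported with its 95% CI, so a reader can see the imprecision, and the code is labelled as an example. All of this stands and limits the weight of the point. It does not rescue the sentence, which draws a firm conclusion that ignores those CIs.

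A reader might infer that Day x is governed by sample size and not by closeness to plateau. The figures do not support that: at n = 20, moving from a 10% to a 15% shortfall cuts the probability from 48-73% to 13-46%.

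A reader might also infer that changing the last contrast to Day 295 repairs the list. It does not, because Table 2 schedules no q8w PK sample on Day 295 either.

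A third tempting step is to prescribe a 90% CI within 0.80-1.25. That range appears nowhere in the documents. At n = 20, log SD 0.2 and four later troughs it would declare steady state more often than the SAP rule: 73% against 48% for a 10% shortfall, and 32% against 13% for 15%. Any range needs its own justification.

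Finally, time need not be the only fixed effect. Doses differ by weight band (Protocol Table 4), so a dose term may be intended.

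**Conclusion.** The concern holds. The rule converts lack of evidence into a dated conclusion, and while troughs are still changing it favours an earlier day when data are sparser or noisier. The direction follows from the rule. The sizes rest on the assumed SDs, shortfalls and accumulation pattern, none of which the documents give. The effect is on the probability of an early Day x and is not certain in any one data set; where troughs are truly flat, the rule is usually right. The mismatch with Table 2, the repeated Day 239 and the inconsistent code are matters of text and need no assumption. This should be corrected, but it does not touch the primary or secondary endpoints.

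**What to change.** 1. Delete the sentence that concludes Day x from the first non-significant comparison. Report each planned ratio of least-squares means with its 95% CI, and describe the approach to plateau from those.
2. If a Day x is still wanted, base it on the CI lying within a range that the sponsor prespecifies and justifies. Otherwise report *not shown*.
3. Restrict the contrasts to troughs scheduled in Protocol Table 2 (Days 15, 71, 127, 183, 351), or reconcile the SAP days with the schedule. Either route must deal with the repeated Day 239.
4. Make the LSMEANS and contrast terms match the MODEL and CLASS statements.

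The cost is SAP wording and a small programming change; items 1, 2 and 4, and item 3 if the contrasts are restricted, need no new data. The downside is that a definite Day x may not be reported, particularly at the interim.
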